#### 8.4.5 Summaries of Baseline Characteristics, and Demographics

The number and percentage of subjects screened, enrolled, the primary reasons for screening failure, and the primary reason for discontinuation will be displayed. Demographic variables, baseline characteristics, primary and secondary diagnoses, and prior and concomitant therapies will be summarized by treatment either by descriptive statistics or categorical tables.

#### 8.4.6 Patient Reported Outcomes (PROs) Evaluation

The FACT-H&N questionnaire will be will be used to assess HRQOL (See 11.7). This questionnaire combines 27 questions from the FACT-G scale with 12 disease specific questions for head and neck cancer. The FACT-H&N can be subdivided into five subscales which include the four subscales of the FACT-G (physical well-being, social/family well-being, emotional well-being, and functional well-being) and the Head and Neck Cancer Subscale. This questionnaire is widely used in head and neck cancer patients and has been validated within this population [22].

The FACT-H&N questionnaire will be requested at defined time points; at baseline, end of treatment, 6 months, 1 year, and 1 years post treatment. The initial questionnaire must be filled out prior to any treatment.

Statistical analysis of HRQOL will involve global HRQOL as well as each of the five domains in the FACT-H&N questionnaire. Longitudinal analysis will be conducted using a linear mixed model to compare the overall score and subscales scores between the patients in this trial and historical controls.

#### 8.4.7 Interim Analyses

A formal interim efficacy analysis will occur after 27 patients have enrolled in the study. This analysis will be reviewed by the DSMB to determine if the study should continue to accrue to a total of 39 evaluable patients. A non-formal safety analysis will occur after approximately 8 patients have completed the study treatment. This analysis will not involve stopping the study. The DSMB will meet and review toxicities at that time point. If it is felt there is risk beyond what is to be expected for standard CRT, the DSMB will determine if the study should be stopped and if a formal safety analysis is warranted.

#### 8.4.7.1 Interim Efficacy Analysis

An interim analysis will also occur to evaluate efficacy. The interim analysis will occur after 27 patients are accrued to the study and have treatment end response assessments completed (imaging and if applicable, salvage surgical resection). This will occur at approximately 9 months after study initiation. In terms of efficacy, futility will be determined if 13 or fewer CRs (rCR +pCR) are seen in the 27 patients. If futility is not determined, the study will continue to accrue to final total of 34 HPV + patients and 23 HPV - patients who are evaluable for treatment response. This will be presented to and evaluated by the DSMB.

## 8.4.7.2 Multiplicity

No multiplicity adjustment is planned.

## 8.4.7.3 Sample Size and Power Calculations

Sample size for this study will be powered based on the co-primary outcome of efficacy. Efficacy will be defined by the rCR rate at the treatment end imaging evaluation. The rCR rate will be defined by RECIST 1.1 criteria. Based on the Intergroup Trial evaluating the gold standard of high-dose bolus cisplatin 100 mg/m2 given on days 1, 22, and 43 of radiation at 70 cGy, the complete response rate was 40.2% [10]. This study included both HPV+ and HPV-patients with unresectable disease and did not differentiate response based on HPV status. Extrapolating on our data from the animal model, we anticipate at least a 50% improvement in this CR rate. Therefore, we estimated a CR rate of 60.4% with this study regimen in all-comers.

For the initial sample size calculation, Simon's two-stage design with the Minimax approach was utilized. The null hypothesis that the true response rate is 0.402 will be tested against a one-sided alternative. In the first stage, 27 patients were to be accrued. If there are 13 or fewer CRs in these 27 patients, the study will be stopped. Otherwise, 12 additional patients will be accrued for a total of 39. The null hypothesis will be rejected if 21 or more CRs are observed in 39 patients. This design yielded a type I error rate of 0.05 and power of 0.80 when the true CR rate is 0.604.

At the time of interim analysis, 27 patients are enrolled in the study. During this analysis, an internal analysis of a similar study (NCT01386632) using standard of care high-dose cisplatin

(100 mg/m2 on days 1, 22, and 43) in a similar cohort of patients was performed. Distinct differences in response were seen in the HPV+ and HPV- groups, which mirror efficacy findings in similar studies. This analysis has revealed that 20 of 27 (74%) of evaluable patients with HPV positive disease achieved a CR (based on 3-month post-radiation CT and/or PET or subsequent salvage surgery).

Based on this new data, we have reassessed our power calculations for our HPV positive cohort, With this novel combination therapy we estimate that an improvement in efficacy of >20% to a CR rate of 90% would warrant future study of this regimen in HPV positive disease. Therefore, using a one-arm binomial design the null hypothesis that the true response rate is 74% will be tested against a one-sided alternative. The null hypothesis will be rejected if 31 or more CRs are observed in 34 patients. This design yields a type I error rate of 0.05 and power of 80% when the true response rate is 90%.

Reviewing the same data, the HPV negative cohort had 6 of 12 (50%) evaluable patients achieving a CR (based on 3-month post-radiation CT and/or PET or subsequent salvage surgery). Therefore, reassessing our power calculations for the HPV negative cohort in the proposed expansion cohort, we estimate a CR rate of 75% (50% improvement from the standard of care) with the study regimen would warrant future study of this regimen in HPV negative disease. Therefore, using a one-arm binomial sample size, the null hypothesis with a true response rate of 50% will be tested against a one-sided alternative. The null hypothesis will be rejected if 18 or more responses are observed in 23 patients. This design yields a type I error rate of 0.05 and power of 80% when the true response rate is 75%.

At the time of the interim analysis, 20 patients with HPV + disease are enrolled and 7 patients with HPV - disease are enrolled. Based on this reanalysis of sample size and power calculations, an additional 14 HPV positive patients and 16 HPV negative patients would need to be enrolled after the interim analysis.

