# 3.0 OBJECTIVE(S) & HYPOTHESIS (ES)

#### 3.1 **Primary Objective(s) & Hypothesis(es)**

1. **Objective:** To determine the safety and tolerability of pembrolizumab given in combination with cisplatin-based chemoradiotherapy (CRT) in subjects with treatment naive Stage III-IVB squamous cell carcinoma of the head and neck (SCCHN).

**Hypothesis**: Pembrolizumab can be safely added to cisplatin-based CRT and will be well tolerated in patients with Stage III-IVB SCCHN.

2. **Objective:** To evaluate the efficacy of pembrolizumab given in combination with definitive CRT by complete response rate at treatment end in patients with HPV+ SCCHN and HPV-SCCHN.

**Hypothesis**: The addition of pembrolizumab to standard CRT will provide a 75% or greater CR rate in patients with Stage III-IVB HPV- SCCHN and a 90% or greater CR rate in patients with Stage III-IVB HPV+ SCCHN.

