## 4.2.3.5 **Preliminary Results and Rationale for Expansion Cohort**

The current study has enrolled 27 patients from November 18, 2015 to August 6, 2016. The study is currently on hold for an interim safety and efficacy analysis. As of the data lock on September 14, 2016, 20 (74.1%) patients with HPV positive (p16 positive) disease and 7 (15.9%) with HPV negative (p16 negative) disease have enrolled. Early response data in imaged patients (n=9), shows a CR (CT and/or PET or pathologic CR on salvage surgery) in 8/8 (100%) of HPV positive patients and a PR in the single HPV negative patient. We anticipate easily hitting our primary endpoint of CR rate >60% in our HPV positive population based on these early results. However, based on our lack of HPV negative patients, it is unclear what responses will be seen.

Recent data analysis of an internal study (NCT01386632) using standard of care high-dose cisplatin (100 mg/m2 on days 1, 22, and 43) in a similar cohort of patients was performed. Distinct differences in response were seen in the HPV+ and HPV- groups, which mirror efficacy findings in similar studies. This analysis has revealed that 20 of 27 (74%) of evaluable patients with HPV positive disease achieved a CR (based on 3-month post-radiation CT and/or PET or subsequent salvage surgery). In the same study, the evaluable patients in the HPV negative cohort had 6 of 12 (50%) achieving the same CR endpoint.

Due to the historically good responses in HPV positive disease and the early findings in our current HPV positive cohort, we propose evaluation of efficacy separately in the HPV positive and HPV negative cohorts. As a result, we propose adding expansion cohorts after the interim analysis to explore efficacy in each of these unique populations. Addition of both HPV negative and HPV positive patients will provide further insight into efficacy of this novel combination.

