#### 5.3 Trial Blinding/Masking

This is an open-label trial; therefore, Sanford Research, investigator and subject will know the treatment administered.

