is estimated that57 evaluable patients, will be	Sample Size and Power	Sample size is based off the efficacy endpoint. It
	1	
		sufficient to determine the efficacy endpoint
with a power $= 0.8$ and one-sided alpha $= .05$ .		

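### Section 8.4.7.3 claims 5% type I error and 80% power for both HPV cohort rules; the exact values are 1.2% and 55% (HPV+) and 0.5% and 47% (HPV-)

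*Combined protocol and SAP*

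**What the plan says.** Section 8.4.7.3 re-plans the study by HPV status, using CR rates from an internal high-dose cisplatin study as the nulls.

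- **HPV+:** null 74% (20 of 27), target 90%, 34 patients. "The null hypothesis will be rejected if 31 or more CRs are observed in 34 patients". The text claims type I error 0.05 and power 80% at a true rate of 90%.
- **HPV-:** null 50% (6 of 12), target 75%, 23 patients. "The null hypothesis will be rejected if 18 or more responses are observed in 23 patients". The text continues: "This design yields a type I error rate of 0.05 and power of 80% when the true response rate is 75" per cent.

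The Section 8.1 table says "Sample size is based off the efficacy endpoint" and gives power 0.8 and one-sided alpha .05 for 57 evaluable patients in total. Section 3.1 makes CR rate in the two HPV groups a primary objective; for HPV- disease the hypothesis is "The addition of pembrolizumab to standard CRT will provide a 75% or greater CR rate in patients", and for HPV+ disease it is 90% or greater. Section 8.4.7.2 states "No multiplicity adjustment is planned".

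**The concern.** For each cohort, Section 8.4.7.3 gives the sample size, null rate, target rate and rejection count. These four numbers fix the type I error and the power, so the claimed 0.05 and 80% can be checked directly.

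The cut-offs look high for a one-sided 5% test. They are the smallest counts whose observed rate reaches the target itself: 31/34 = 91.2% (30/34 = 88.2% falls short of 90%) and 18/23 = 78.3% (17/23 = 73.9% falls short of 75%). A rule that requires the observed rate to reach the assumed true rate has power near one half, whatever the sample size.

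The stated power supports the choice of 34 and 23 patients, and the rules bear on whether the regimen warrants further study. If the power is wrong, a missed cut-off will be read as a negative result from an 80%-power design when it is close to a coin toss for a regimen performing at target.

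**Working it through.** **Inputs (all from Section 8.4.7.3).** HPV+: n = 34, reject at 31 or more, p0 = 0.74, p1 = 0.90. HPV-: n = 23, reject at 18 or more, p0 = 0.50, p1 = 0.75.

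**Formula.** With X ~ Binomial(n, p), type I error = P(X ≥ r | p0) and power = P(X ≥ r | p1), where P(X ≥ r | p) = Σ C(n,k) p^k (1−p)^(n−k) for k = r to n.

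**1. What reproduces.** The initial Simon two-stage rule (stop at 13 or fewer of 27; reject at 21 or more of 39; 40.2% vs 60.4%) gives type I error 0.0498 and power 0.801, as claimed. The cohort sample sizes also reproduce from the one-sided arcsine formula n = [(1.645 + 0.842)/(2·asin√p1 − 2·asin√p0)]²: 33.97, rounded up to 34, and 22.55, rounded up to 23.

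**2. The stated cut-offs.**

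- HPV+, power at 0.90, for k = 31 to 34: 0.2283 + 0.1926 + 0.1051 + 0.0278 = **0.554**. Type I error at 0.74: 0.00929 + 0.00248 + 0.00043 + 0.00004 = **0.0122**.
- HPV-, type I error at 0.50: (33649 + 8855 + 1771 + 253 + 23 + 1)/2^23 = 44552/8388608 = **0.0053**. Power at 0.75, for k = 18 to 23: 0.1853 + 0.1463 + 0.0878 + 0.0376 + 0.0103 + 0.0013 = **0.468** (from unrounded terms).

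The chance of missing the cut-off at the target rate is 1 − 0.554 = 45% and 1 − 0.468 = 53%. Power reaches 80% only if the true CR rate is about 93.2% (HPV+) or 82.6% (HPV-).

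**3. Other readings.** Using p0 = 20/27 gives HPV+ type I error 0.0125. Requiring more than 31 and more than 18 lowers power to 32.6% and 28.3%. Normal approximations at the stated cut-offs, with or without continuity correction, give power of 41–52% and 36–45%. None gives 80%.

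**4. Neighbouring cut-offs (exact).**

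| Cohort | Rule | Type I error | Power |
|---|---|---|---|
| HPV+ | ≥31/34 (stated) | 0.0122 | 0.554 |
| HPV+ | ≥30/34 | 0.0375 | 0.750 |
| HPV+ | ≥29/34 | 0.0909 | 0.881 |
| HPV- | ≥18/23 (stated) | 0.0053 | 0.468 |
| HPV- | ≥17/23 | 0.0173 | 0.654 |
| HPV- | ≥16/23 | 0.0466 | 0.804 |

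For HPV-, 16 of 23 gives what the plan claims. For HPV+, no cut-off at 34 patients combines exact type I error of at most 0.05 with 80% power. The smallest n that does is 38 (≥33/38: 0.0459, 0.825).

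**5. Cost of lower cut-offs.** With independent cohorts and both nulls true, the chance of at least one false positive is 1 − (1 − 0.0122)(1 − 0.0053) = 0.017 now, and 1 − (1 − 0.0375)(1 − 0.0466) = 0.082 with 30/34 and 16/23.

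Section 4.2.3.5 reports a "CR (CT and/or PET or pathologic CR on salvage surgery) in 8/8 (100%) of HPV positive patients". If all eight count towards the 34, 26 patients remain. Under the 74% null, the chance of HPV+ success is then P(X ≥ 23 | 26) = 0.065 with the cut-off at 31, and P(X ≥ 22 | 26) = 0.156 with it at 30. At a true rate of 90% the figures are 0.741 and 0.888.

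**The case against.** The arithmetic is not in dispute. The case on the other side concerns framing, scope and remedy.

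- **The 5% limit is not breached.** Read as a ceiling, 0.05 is respected by 1.2% and 0.5%. This stands: the material defect is power.
- **The sample sizes are not the main fault.** This largely stands. Both reproduce from a standard formula, and 23 is adequate for HPV- with the cut-off at 16. For HPV+, 34 falls short on exact calculation, with 75% power at best.
- **The rules may not govern the conclusion.** Section 8.1 calls the key analysis estimation with no statistical hypothesis, and Section 8.4.3.1 tests the CR rate in all subjects against 40.2%. The documents do conflict here. But Section 3.1 makes CR by HPV group a primary objective, and the conflict does not make the stated power true.
- **Section 8.1 names no cohort rule.** Correct: it gives 0.8 and .05 for 57 patients overall. Since the 57 are the 34 plus the 23, that line needs correcting too.
- **The high cut-offs may be deliberate,** so that success requires an observed rate at the target. That would fit Section 3.1, but the documents do not say so, and the power claim would still be wrong.
- **Lowering the cut-offs is risky.** This stands, and is why that route is secondary.

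**Conclusion.** The concern holds. The stated cut-offs have exact one-sided type I error 0.012 and power 55% (HPV+), and 0.005 and 47% (HPV-), against the claimed 0.05 and 80%. Power is about 25 and 33 percentage points short. The rules are conservative, so a positive result would not be undermined; a negative one would be over-read.

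These figures rest only on the plan's own n, cut-offs and rates, with independent responses and all 34 and 23 patients evaluable. The joint false-positive figures also assume independent cohorts with both nulls true. The conditional HPV+ figures assume that the eight reported CRs count towards the 34.

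A linked gap remains: Section 8.4.3.1 and Table 7 name no test against 74% or 50%. The asymptotic one-sided 5% test named there would, applied to these nulls, reject from 30/34 and 16/23, so it does not explain 31 and 18 either.

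**What to change.** **Preferred: keep the cut-offs and correct the claims.** In Section 8.4.7.3, state exact one-sided type I error 0.012 and power 55% at a true rate of 90% for ≥31/34, and 0.005 and 47% at 75% for ≥18/23. Align the Section 8.1 line. If the cut-offs were chosen so that the observed rate must reach the target, say so. The cost is wording only, but the protocol then admits 55% and 47% power.

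**Alternative, if the sponsor wants to use the 5% allowance:** change the cut-offs to ≥30/34 (type I error 0.038, power 75%) and ≥16/23 (0.047, 80%), and restate HPV+ power as 75%. Section 5.3 says "This is an open-label trial" and responses have already been seen, so this must be a dated amendment made before the final cohort CR counts are reviewed. It should disclose:

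- the 8/8 HPV+ CRs and any responses seen since that data lock;
- that success would be declared at observed rates below target (30/34 = 88.2%, 16/23 = 69.6%);
- that the chance of at least one false-positive cohort rises from 1.7% to 8.2% with no multiplicity adjustment.

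No extra patients are needed if 75% is accepted. Holding 80% for HPV+ takes at least 38 patients, four more. That margin is fragile: exact power at 5% drops to 79.4%, 77.7% and 76.0% at n = 40, 41 and 42.

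**Under either route,** add to Section 8.4.3.1 and Table 7 an exact one-sided binomial test of each cohort's CR rate against 74% (HPV+) and 50% (HPV-).

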#### 8.4.7.4 Subgroup Analyses and Effect of Baseline Factors

All efficacy endpoints CR rate, ORR, PFS, OS, LRC rate, and DM rate will be evaluated and compared based on:

- HPV-positive and HPV-negative status
- PD-L1 positive and PD-L1 negative status
- Additional correlative studies as pertinent
- ECOG PS 0 or 1
- Key demographic variables (i.e. age, sex, etc.) as deemed appropriate

Differences in subgroups will be evaluated using appropriate statistical techniques adjusting for key demographic variables. Models will include logistic regression and proportional hazards regression.

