#### 3.2 Secondary Objective(s) & Hypothesis (es)

1. **Objective:** To estimate progression-free survival (PFS), overall survival (OS), the locoregional control rate (LRC), and distant metastases (DM) rate at 1- and 2-years in subjects treated with pembrolizumab given in combination with CRT.

**Hypothesis**: The addition of pembrolizumab to standard CRT will show increased efficacy in terms of key survival endpoints utilized in head and neck cancer.

2. **Objective:** To determine the best overall response rate (ORR) as defined by RECIST 1.1 at treatment end imaging in subjects with Stage III-IVB SCCHN treated with pembrolizumab given in combination with CRT.

**Hypothesis**: The addition of pembrolizumab to standard CRT will show superior ORR compared to historical controls.

4. **Objective:** To estimate the quality of life (QOL) of subjects with Stage III-IVB SCCHN treated with pembrolizumab in combination with CRT during therapy, treatment end, and 1- and 2-years following treatment.

**Hypothesis**: Acute and long-term QOL of participants treated with the combination of pembrolizumab and low dose weekly cisplatin and radiation will be superior to historical controls.

5. **Objective:** To correlate ORR, PFS, OS, LRC, and DM with tumor PD-L1 expression in subjects with Stage III-IVB SCCHN treated with pembrolizumab in combination with CRT.

**Hypothesis**: High PD-L1 expression has correlated with responses in the metastatic setting and will correlate with key disease response and survival outcomes in the curative intent setting.

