#### **3.3 Exploratory Objectives**

To determine the genomic, transcriptomic, and proteomic profile of subjects' tumors to identify gene mutations, gene amplifications, RNA-expression levels, and protein-expression levels. Additional analysis will evaluate peripheral blood immune response utilizing similar techniques. Correlations between genomic, transcriptomic, and proteomic profiles and efficacy outcomes will be assessed.

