#### 4.2.3.2 Pharmacokinetic, Biomarker, and Patient Report Outcomes Research

There are ongoing clinical trials evaluating pembrolizumab in combination with platinumdoublet therapy in non-small cell lung cancer and in other chemotherapy combination studies [31]. This will be the first study looking at pembrolizumab in combination with weekly cisplatin chemotherapy. Despite this, based on data from other combination studies, the risk for a drug-drug interaction is extremely low. Furthermore, pembrolizumab has been utilized with cisplatin at varying doses in a number of studies with accompanying pharmacokinetic data. As a result, pharmacokinetic data will not be obtained during this study. Additionally, as it is felt there is reasonable data available to understand the risk of anti-drug antibodies with this combination. Therefore, this will also be excluded from this protocol.

PD-L1 expression may be an important factor in efficacy. Current data supports high PD-L1 expression as a correlate of response to therapy. While patients with no or low expression may still respond to pembrolizumab, the response rates are significantly higher for those with high expression. As we venture into multimodality therapy with chemotherapy and radiation, it will be important to see if baseline expression of PD-L1 correlates with a response. As previously mentioned, data is emerging that suggests altered PD-L1 expression during both chemotherapy and radiation. While we will not be performing biopsies during therapy, the baseline PD-L1 expression may be important to see if this biomarker maintains its predictive nature in the setting of chemoradiation. There is the potential that the biomarker will not continue to predict response, as even non-expressers or low expressers at baseline, may develop enhanced responses during CRT. It will be important to evaluate PD-L1 expression to generate hypotheses for future biomarker research.

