#### 7.1.3.1 **Tissue Collection and Evaluation**

#### 7.1.3.1.1Tumor Collection for p16, PD-L1, and Genomic Analysis

All subjects will have p16 immunohistochemical (IHC) staining (high risk HPV DNA testing may be used as outlined in section 5.1.2) done per institutional standard procedures prior to treatment.

All subjects will submit a recently obtained core or excisional biopsy (within 60 days from enrollment). Fine-needle aspirates (FNAs) are not adequate. Characterization of PD-L1 will be performed using IHC. Detailed instructions for processing of specimens and testing are outlined in the procedures manual and statistical analysis plan (SAP).

For correlative genomic studies, tumor tissue blocks will be micro-dissected and Tumor DNA and RNA will be immediately processed and stored. Detailed instructions for processing of tumor specimens and testing are outlined in the SAP.

For infiltrating immunocyte analysis, tumor tissue blocks will be stored in the Sanford or similar UCSD facility and testing will be completed at a later date. Detailed instructions for processing of tumor specimens are outlined in the SAP.

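### Secondary objective 5 concerns PD-L1 expression, but the only analysis form specified is positive versus negative, with no scoring method or cut-off stated

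*Combined protocol and SAP*

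**What the plan says.** Section 3.2, objective 5, is "To correlate ORR, PFS, OS, LRC, and DM with tumor PD-L1 expression". Its hypothesis is framed by level: "High PD-L1 expression has correlated with responses in the metastatic setting". Section 4.2.3.2 also grades expression: "While patients with no or low expression may still respond to pembrolizumab, the response rates are significantly higher for those with high expression". PD-L1 is the only tissue or blood marker with a secondary objective of its own. The molecular profiles are exploratory (section 3.3): "Correlations between genomic, transcriptomic, and proteomic profiles and efficacy outcomes will be assessed".

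The analysis is in section 8.4.7.4: "All efficacy endpoints CR rate, ORR, PFS, OS, LRC rate, and DM rate will be evaluated and compared based on" a list of factors, one of which is "PD-L1 positive and PD-L1 negative status". The same section adds: "Models will include logistic regression and proportional hazards regression". Table 7 has no PD-L1 row.

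On measurement, section 7.1.3.1.1 says: "Characterization of PD-L1 will be performed using IHC". It refers to the procedures manual and the SAP for specimen handling and testing. No scoring system, positivity cut-off or expected prevalence appears in the supplied text. Section 7.1.2.7.1 says that PD-L1 is characterized retrospectively, and section 5.3 that the trial is open-label.

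**The concern.** The objective and its rationale are about how much PD-L1 a tumor expresses. The analysis asks only which side of an unstated line the tumor falls on. Under that coding, two patients just either side of the line count as opposites, and two far apart on the same side count as identical. In a trial of 57 patients this could lose a good part of what the marker can tell.

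The missing cut-off is a second problem. PD-L1 is read retrospectively, all parties know the treatment, and response data from the first patients were already in hand when the expansion was planned (section 4.2.3.5). Nothing in the supplied text requires the line to be fixed before outcomes are known. By contrast, p16 positivity does have a stated staining cut-off, above 70% of tumor cells (section 5.1.2).

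**Working it through.** **The plan's own figures.** The documents give no power or precision for PD-L1. The only sample size is 57 = 34 HPV-positive + 23 HPV-negative (section 8.4.7.3), with one-sided alpha 0.05 and power 0.80. The one-sample arcsine formula n = [(1.645 + 0.842) / (2·asin√p1 − 2·asin√p0)]² reproduces it:
- HPV-positive, 74% against 90%: (2.487/0.4266)² = 33.97, so 34.
- HPV-negative, 50% against 75%: (2.487/0.5236)² = 22.55, so 23.

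So N = 57 was set for the complete response (CR) rate and not for PD-L1.

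**Information kept by two groups.** Assume a normal score X with a linear effect, and let q be the share called positive. The information kept, relative to using X itself, is the squared correlation between X and the indicator X > c: φ(c)² / [q(1 − q)], where c is the (1 − q) normal quantile. At q = 0.5 this is 0.3989²/0.25 = 0.637 (that is, 2/π). At q = 0.2 it is 0.2800²/0.16 = 0.490.

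| Share positive | Kept | Lost | Effective N of 57 |
|---|---|---|---|
| 50% | 0.637 | 36% | 36.3 |
| 30% | 0.576 | 42% | 32.8 |
| 20% | 0.490 | 51% | 27.9 |
| 10% | 0.342 | 66% | 19.5 |
| 5% | 0.224 | 78% | 12.8 |

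The equivalent number of patients lost is 57 − 36.3 = 20.7 at the median split and 57 − 27.9 = 29.1 at 20/80.

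**Other assumed shapes.** A uniform score cut at its median loses 25%. Scores with 20% to 60% of patients at zero and a skewed remainder, cut at 1, 10, 20 or 50 on a 0–100 scale, lose between 12% and 70%, depending on the cut and on whether the effect is linear in the raw or the log score. With the 5%-positive normal case, the overall range is about 12% to 78%.

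**Illustrative power** (all effect sizes assumed, two-sided 0.05):
- Progression-free survival with 20 events and a hazard ratio of 1.8 per SD. Power = Φ(ln 1.8 × √(20 × kept) − 1.96). Continuous: Φ(2.629 − 1.96) = 75%. Median split: Φ(2.097 − 1.96) = 55%. 20/80 split: Φ(1.840 − 1.96) = 45%.
- CR, n = 57, odds ratio 2 per SD, simulated score test. At a 60% CR rate: 67% continuous, 49% at a median split, 33% at 20/80. If the design alternatives are met, the pooled CR rate is (34 × 0.90 + 23 × 0.75)/57 = 47.85/57 = 84%, which leaves about 9 patients without a CR. Power is then 44% continuous and 29% at a median split.

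**The case against.** Several objections have force.

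- **The plan does not exclude a continuous analysis.** Objective 5 is worded as a correlation with expression, and logistic and proportional hazards models accept a continuous term. That stands: positive versus negative is the only form specified, not the only form allowed.
- **Further detail may exist elsewhere.** Sections 7.1.3.1.1, 8.1 and 8.2 refer to a fuller SAP, and section 7.1.3.1.1 also to the procedures manual. A missing cut-off here does not prove that none was set. That stands too, and it limits the point to the supplied text.
- **The hypothesis may describe a threshold.** High against low or no expression fits a step at least as well as a straight line. If the step lies at the cut, two groups lose little and a linear term may fit worse. This is a reason to report both codings. It does not support leaving the cut undefined.
- **The analysis is hypothesis-generating.** Section 4.2.3.2 says so, and section 8.4.3.1 plans intervals, not formal tests, for secondary endpoints. Power is therefore only an illustration, and with about 9 non-responders it is low under either coding. The loss of information widens intervals in the same way.

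A reader might also infer that the cut will be picked to fit the outcomes. Simulating the best-fitting cut between the 20th and 80th percentiles with n = 57 and 9 or 20 non-responders gives a false-positive rate of roughly 26% to 32% in place of 5%, depending on the test. But no section plans such a search. The documents support only the weaker statement that nothing in them rules it out.

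**Conclusion.** The point holds in a limited form. The specified PD-L1 comparison is narrower than objective 5, and its groups are undefined in the supplied documents. Neither statement needs a distributional assumption.

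The size of the loss does. The range of 36% to 51% requires a recorded continuous score, a normal distribution, a linear effect and a positive share between 20% and 80%. The documents state none of these, nor that IHC yields a percentage. It would be wrong to read a loss of a third to a half as a fact about this trial: the assumed alternatives span about 12% to 78%, and a threshold effect at the cut would cost little.

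Nor should a reader infer that a continuous score would show whether PD-L1 keeps the predictive role discussed in section 4.2.3.2. Every patient receives pembrolizumab (section 5.4), so neither coding can separate a predictive from a prognostic effect.

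**What to change.** In section 8.4.7.4:

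1. Name the PD-L1 scoring system and require that the IHC score itself be recorded, as a percentage or ordinal grade.
2. Make that score, as a continuous or ordinal term (log- or rank-transformed if skewed), the analysis for objective 5 in the logistic and proportional hazards models already listed.
3. Keep the positive/negative comparison as descriptive, and state its cut-off before PD-L1 results are linked to outcomes.
4. Report both codings, since a linear term can fit less well than a split if the effect is a true threshold.
5. Describe the result as an association in treated patients, not as evidence of a predictive effect.

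The cost is mainly wording. No patients or biopsies are added, and the primary analysis is unchanged. If the laboratory reports only positive or negative, it would also have to supply the score; the documents do not show whether it already does.
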